Surveillance for enteric fever will be undertaken at the Maniknagar field office and Mugda Medical College and Hospital for all age-eligible (from 6 months to 15 years) residents recorded in the baseline list. Participants with a subjective history of ≥2 days of fever and/or a temperature of ≥38°C at presentation will be enrolled in the surveillance. A blood sample (3ml) will be collected for microbiological culture. The participants will receive appropriate clinical management. Blood culture-positive patients will be visited at home to confirm their identity, and collect information about their illness and patients will be asked to visit the field office if their condition is not improved. The treatment will be adjusted as necessary, based on laboratory testing.

Study staff will visit households, included in the baseline listing, periodically, to remind them to seek treatment at the Maniknagar field office if their children (both vaccinees and non-vaccinees) develop a fever.

Eligibility criteria for enrollment in the passive surveillance

- Participants information, available in the listing database
- Parent/guardian is willing and competent to provide informed consent. For participants aged 11 to 15 years, informed assent will also be considered
- Participants from the study area who experienced a fever lasting for ≥2 days and/or temperature ≥38°C at presentation [4, 30]
- Participants aged 6 months to 15 years on the first day of the vaccination campaign

Flow diagram

Laboratory procedures

Passive surveillance samples

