SOP and training																						
materials																						
development																						
Training for																						
vaccination and																						
surveillance																						
Listing of																						
interested children																						
for vaccination in																						
the study area																						
Vaccination																						
AEFI recording																						
SAE recording																						
and reporting																						
Diary card review																						
Patient enrollment																						
in the passive																						
surveillance																						
Patient																						
management																						
Sample collection																						
for imunogenicity																						
and passive																						
surveillance																						
Laboratory																						
analysis																						
Data cleaning																						
Development of																						
statistical analysis																						
plan																						
Data analysis																						
Clinical study																						
report (CSR)																						
development																						
Manuscript																						
writing and																						
submission																						
Dissemination of																						
findings in																						
national and																						
	 	1	1	 	 	l	l	l	1									1	1	1		

international											
community											

Sample Size Calculation and Outcome (Primary and Secondary) Variable(s)

Clearly mention your assumptions. List the power and precision desired. Describe the optimal conditions to attain the sample size. Justify the sample size that is deemed sufficient to achieve the specific aims.

A sample size of 515 (103 cases and 412 controls) will be required in this case-control test-negative design study assuming vaccine effectiveness of 80%, vaccine coverage of 65% in the target age-eligible population (6 months to 15 years), 4 controls per case, precision width of \pm 10% (20%) and type 1 error rate of 0.05. Considering the incidence rate for typhoid fever of 230 per 100,000 person-years among the non-vaccinated population aged 6 months to 15 years, the target number of vaccinations is \sim 60,000.

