To achieve the target number of vaccinees aged 6 months to 15 years representing \sim 31% of the total population), the required age-eligible children and population of all age groups will be \sim 92,000 and \sim 297,000 respectively.

Data Analysis

Describe plans for data analysis, including stratification by sex, gender and diversity. Indicate whether data will be analysed by the investigators themselves or by other professionals. Specify what statistical software packages will be used and if the study is blinded, when the code will be opened. For clinical trials, indicate if interim data analysis will be required to determine further course of the study.

Focal time

Focal time will be defined as the date of onset of symptoms leading to presentation for care.

Culture-positive case

Eligible febrile patients who will be positive by blood culture for *Salmonella enterica* serotype Typhi and symptoms developed >14 days after vaccination, or, if unvaccinated, >14 days after the midpoint of the vaccination period.

Culture-negative control

Eligible febrile patients who will be negative by blood culture for *Salmonella enterica* serotype Typhi and symptoms developed >14 days after vaccination, or, if unvaccinated, >14 days after the midpoint of the vaccination period. Given that the sensitivity of the blood culture method is ~59% [36], we will apply the clinical rule, defined in a previous analysis for blood culture-negative typhoid patients, to exclude clinical typhoid patients from the analysis [37]. This exclusion will be helpful for a better evaluation of the magnitude of protection conferred by the vaccine in the proposed study.

Matching of cases and controls

A statistician, blinded to the vaccination status of participants will select blood culture-negative controls (after excluding clinical typhoid patients, vide supra) against each case. Matching of controls for each case will then be done considering the age groups at focal time (6 months to <2 years; 2 to 4 years; and 5 to 15 years) and date of presentation. Controls will be randomly selected on the day of the presentation; if matched controls will not be available on that day, the selection period will be widened for up to a maximum of ± 7 days.

Statistical analysis

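### Eligible culture-negative children beyond the matched draw never enter the primary analysis, and the 103-case target comes from an unmatched formula that the planned 1:4 conditional model does not quite meet

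*Protocol*

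**What the plan says.** - **Surveillance for enteric fever:** listed children who meet the fever definition at either of the two facilities are enrolled, and "A blood sample (3ml) will be collected for microbiological culture". Culture is not restricted to a sample of them.
- **Sample Size Calculation:** "A sample size of 515 (103 cases and 412 controls) will be required in this case-control test-negative design study". The assumptions are "vaccine effectiveness of 80%, vaccine coverage of 65% in the target age-eligible population", "4 controls per case", a total interval width of 20 points, and a type 1 error rate of 0.05.
- **Culture-negative control:** culture-negative children who meet a clinical rule for typhoid are removed before controls are chosen.
- **Matching of cases and controls:** a statistician blinded to vaccination status matches on three age bands and presentation date. "Controls will be randomly selected on the day of the presentation; if matched controls will not be available on that day", the window may widen to 7 days either side. This section gives no number of controls per case.
- **Statistical analysis:** conditional logistic regression on matched status. The shell table has columns for cases and matched controls only.

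**The concern.** Sampling controls saves money when each control costs something to recruit or test. Here every eligible culture-negative child has already been consented, bled and cultured, and is on the listing database, so vaccination status can be linked. Leaving such children out saves almost nothing.

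Cases are the scarce resource. The protocol's own rates imply about as many cases as the target and no reserve. The target was also computed with a formula for unmatched data, whereas the planned model conditions on small matched sets and gains nothing from a set whose members all share one vaccination status. At stake are whether the stated precision is reached, how wide the already sparse age-band and six-month intervals are, and whether the estimate depends on which controls happened to be drawn.

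**Working it through.** **Inputs (all from the Sample Size Calculation section).** Effectiveness 80%, so OR = 0.20; coverage p0 = 0.65; 4 controls per case; total 95% interval width 20 points; "incidence rate for typhoid fever of 230 per 100,000 person-years among the non-vaccinated population"; about 92,000 eligible children, of whom about 60,000 are vaccinated.

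**1. Reproduce the stated figure.**
- Vaccinated share among cases: p1 = 0.2 × 0.65 / (0.35 + 0.2 × 0.65) = 0.13/0.48 = 0.2708.
- Interval width = OR × (e^h − e^−h) = 2 × OR × sinh(h), with h = 1.96 × SE. A width of 0.20 needs sinh(h) = 0.5, so SE = 0.2455 and SE² = 0.0603.
- Unmatched variance per case with M controls: 1/(0.2708 × 0.7292) + 1/(M × 0.65 × 0.35) = 5.064 + 4.396/M.
- At M = 4: 6.163/0.0603 = 102.2, rounded up to 103 cases and 412 controls. This matches the protocol exactly.

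**2. The model actually planned.** For a set of one case and M controls, k of them vaccinated, the conditional information is q(1 − q), where q = 0.2k / (0.2k + M + 1 − k). This is averaged over k, taking the same coverage in every set.
- Sets with uniform vaccination status at M = 4: 0.65⁴ × 0.2708 + 0.35⁴ × 0.7292 = 0.048 + 0.011 = 5.9%. These add no information.
- Mean information per set is 0.153, so the variance per case is 6.53, and 6.53/0.0603 = 108.4, or 109 cases.
- At 103 cases: h = 1.96 × √(6.53/103) = 0.494, giving a width of 20.6 points (67.2% to 87.8%).

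**3. Expected cases.** Over one year with full ascertainment (assumption): 32,000 × 0.0023 + 60,000 × 0.0023 × 0.2 = 73.6 + 27.6 = 101.2. At 101 cases the 1:4 conditional width is 20.8 points.

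**4. Effect of more controls per case.**

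| Controls per case | Cases for 20 points, unmatched | Cases for 20 points, conditional | Conditional width at 101 cases |
|---|---|---|---|
| 4 | 103 | 109 | 20.8 |
| 5 | 99 | 103 | 20.2 |
| 9 | 93 | 94 | 19.2 |
| 19 | 88 | 89 | 18.6 |
| 49 | 86 | 86 | 18.3 |

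With unlimited controls the floor is 84.0 cases by the unmatched formula, and the width at 103 cases is 17.9 points. The largest possible narrowing at 103 cases is therefore from 19.9 to 17.9 points (10%) on the unmatched formula. On the conditional model it is from 20.6 to 18.1 at 49 controls per case (12%), and just under 13% at the floor. Sets are taken as equal in size; unequal sets would gain somewhat less.

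**5. Is there a surplus?** The protocol gives neither culture positivity nor a count of test-negatives. Assumed positivity of 2%, 5%, 10% and 20% leaves 49, 19, 9 and 4 negatives per case. If the clinical rule removed half of them (assumption), these become 24.5, 9.5, 4.5 and 2.

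**6. A tempting alternative that does not work well.** Fixed strata of age band by calendar fortnight (78 strata over a year, patients spread evenly, Mantel-Haenszel estimate) were simulated. Median widths were about 22.5 to 22.9 points with 103 cases at 4 controls per case, 21.3 to 21.5 with 92 at 9, and 20.5 to 20.6 with 88 at 19. All miss 20 points, because controls in strata without a case are wasted.

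**The case against.** **No cap is written.** The matching section sets no number; four is only the planning ratio in the sample size section. A reader might infer that the protocol fixes a cap of four and orders the rest discarded. It does neither in words. What stands is that the random draw, the matched model and the matched-only shell table together leave unselected negatives out, whatever number is drawn. A statistical analysis plan may well settle the ratio, but one that used all negatives would depart from the draw the protocol describes.

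**The surplus is unproven.** This is correct. At about 20% positivity, or after heavy clinical-rule exclusion, there may be none. One cannot say that the trial's own data show the interval to be wider than necessary. If there is no surplus, using all eligible negatives costs nothing in the case-centred analysis.

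**Date matching has a purpose.** Season matters, early visits may overlap the build-up of coverage, and the protocol expects a national campaign soon. It would be too strong to say that coverage is constant over follow-up and that date can be ignored. Calendar time must stay in the analysis, but that does not require a random draw inside the window.

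**The gain is modest.** This also stands.

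**Conclusion.** The point holds as an efficiency weakness that should be corrected. At the protocol's own assumptions, the planned 1:4 conditional analysis narrowly misses its stated precision: about 109 cases are needed against 103 stated and about 101 expected, giving a width of 20.6 to 20.8 points instead of 20. If usable negatives exceed four per case, including them recovers this: at 101 cases the width is 19.2 points with nine per case and 18.6 with nineteen. The ceiling is about 10% of width on the unmatched formula and 12 to 13% on the conditional one.

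Two stronger readings are not supported. The 103 is not an arithmetic slip, since it reproduces exactly from the unmatched formula. Nor does the draw bias the estimate, since selection is random within age band and date and blind to vaccination status.

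The figures assume 80% effectiveness, 65% coverage that is the same in every set, equal set sizes, one year of follow-up and full ascertainment. Any gain from extra controls also assumes a surplus that the protocol does not quantify.

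**What to change.** 1. **Matching of cases and controls:** replace the random draw with all eligible culture-negative children left after the clinical-rule exclusion. Either (a) include all those in the case's age band within the 7-days-either-side window already allowed, assigning each child to one set only because windows of nearby cases overlap, or (b) fit an unconditional logistic model to all eligible children, adjusted for age band and calendar time. Name one as primary. Do not use fixed age band by fortnight strata.
2. **Sensitivity analysis:** keep the 1:4 matched conditional analysis, and state the ratio in the matching section.
3. **Sample Size Calculation:** restate the required cases under the model that will be fitted. For case-centred conditional sets this is about 109 at 4 controls per case, 103 at 5, 94 at 9 and 89 at 19. Do not carry over the unmatched values of about 92 and 88 for the last two.
4. **Shell table:** report all analysed controls, not only a drawn subset.

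Make the change before vaccination status is linked to culture results. The cost is wording, some further linkage and cleaning of records already held, and a less favourable stated target at 4:1 (109 instead of 103). It adds no child, sample or visit.

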The WHO recommended that endemic countries consider the programmatic use of vaccines, to target only the highrisk groups and populations for most countries with the strategies of school- or community-based vaccination or as appropriate depending on the local context such as disease incidence, age-specific disease burden, and percent of school enrollment population. Vaccination is also recommended for outbreak control [6]. In response to an outbreak of XDR Salmonella Typhi, that occurred in November 2016, in Hyderabad, Pakistan, the Aga Khan University Karachi in collaboration with the Ministry of health Sindh had initiated a mass immunization campaign with Typbar-TCV vaccine targeting children aged 6 months to 10 years [7]. Pakistan was the first country to introduce the Typhoid Conjugate Vaccine (TCV) into its routine immunization schedule in 2019 with GAVI Support. Following Pakistan, several other countries including Liberia, Malawi, Nepal, Zimbabwe (GAVI Supported), and Samoa (without GAVI support) have also incorporated TCV into their routine immunization programs [8, 9]. Currently, GAVI approved the vaccination campaign in Bangladesh to cover children aged 9 months to <16 years. Considering the global incidence, a huge bulk of WHO-prequalified vaccines is needed to control the disease. Different vaccine manufacturers step up to mitigate the short supply of the vaccine. Moreover, the 62nd ICC approved the TCV vaccine application, and the request was sent to the Gavi Secretariat on September 13, 2022. Since the TCV is going to be rolled out in Bangladesh with Gavi's support soon, it would be considered unethical to conduct a randomized controlled trial for the TCV. The testnegative design (TND) approach allows researchers to leverage existing data and infrastructure without the need for extensive experimental settings and additional resources. In India, there are four licensed vaccines for typhoid fever. The ZyVac® TCV is one of them which was manufactured by Zydus Lifesciences Limited, Ahmedabad, India. There are several preclinical and clinical trials conducted using this vaccine. Currently, the company has applied for WHO pre-qualification which requires an effectiveness study. The purpose of this study is to evaluate the effectiveness of the typhoid conjugate vaccine (TCV) among Bangladeshi children using the TND.

Currently available typhoid vaccines

Inactivated whole-cell vaccine

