- Parent/guardian is willing and competent to provide informed consent (if the participant is 11 to 15 years of age, assent will also be sought)
- Participants aged between 6 months to 15 years (i.e. up to 15 years 364 days) at the time of vaccination
- Apparently healthy (no complaints of febrile illness) on the day of vaccination
- Parent/guardian confirms that their child will be willing and be able to comply with study requirements

Exclusion criteria for vaccination:

The participant will not be enrolled if any of the following criteria apply:

- Has knowingly received a typhoid vaccine in the past
- Known allergy to any vaccine in the past
- Medical or social reasons that will prevent the participant from conforming to the study requirements as judged by a medical professional
- Planning to move away from the catchment area within the next 12 months
- Pregnant at the time of vaccination, as confirmed by a urine test (urine pregnancy test will be done in girls who are married)
- Confirmed or suspected immunosuppressive or immunodeficiency disorder; or subjects on any immunosuppressive or immunostimulant therapy
- Subject participated in another clinical study in the past 3 months

Temporary exclusion criteria for vaccination:

Participants will be temporarily excluded from being vaccinated if, at the point of vaccination, any of the following apply:

- Receipt of any other vaccines in the last 30 days
- Current temperature of at least 38°C or reported fever within 24 hours prior to vaccination
- Use of antipyretics within 4 hours prior to vaccination
- Unmarried girls between the ages of ≥12 to 15 years old whose first day of their last menstrual period (LMP) is more than 28 days ago or who do not know the date they last menstruated upon presentation

If these apply, the participant will be temporarily excluded from vaccination until the temporary exclusion criteria no longer apply. Please note, for children with fever above 38° C this must be a minimum of 48 hours after the fever has resolved. Unmarried girls between the ages of ≥ 12 to 15 years whose first day of their LMP is more than 28 days or who do not know the date they last menstruated upon presentation will be asked to return after starting their next

menstruation for vaccination. A re-assessment will be conducted to ensure these temporary exclusion criteria no longer exist.

Verification of the potentially eligible children

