For the evaluation of vaccine protection, a conditional logistic regression model will be used, considering matched case-control status as the outcome and vaccination status and selected covariates as independent variables, taking non-receipt of vaccine as the referent category for assessment of vaccine protection. Odds ratios for the associations between vaccination and typhoid fever will be estimated by exponentiation of the coefficient for vaccination from the fitted model, and the standard error of the coefficient will be used to calculate 95% confidence intervals for the estimated effect. Protective effectiveness will be calculated as $[(1 - \text{odds ratio}) \times 100\%]$. The threshold of statistical significance will be considered at P < 0.05.

Analysis of immunogenicity and safety data

Geometric Mean Titres (GMT) and seroconversion rate (≥4-fold rise of anti-Vi-IgG antibody titre induced on day 30 compared to day 0 before vaccination) of anti-Vi-IgG antibody titre will be calculated. Analysis of covariance will be used to adjust for imbalances in baseline titres.

In addition, descriptive analyses of safety data will be done for AEFI or SAEs cases.

Shell table for effectiveness of the typhoid conjugate vaccine against culture-confirmed typhoid cases

	Typhoid C	Cases	Matched c	ontrols	Vaccine effectiveness (VE) (95% CI)					
Overall period	Vaccinees n/N (%)	Non- vaccinees n/N (%)	Vaccinees n/N (%)	Non- vaccinees n/N (%)	Crude VE	P value	Adjusted VE	P value		
All ages	 	I	 	I	 	 		 		
6 months - <2 years										
2 - 4 years										
5 - 15 years										
First six months										
All ages										
Second six mont	hs									
All ages										

Data Safety Monitoring Plan (DSMP)

All clinical investigations (research protocols testing biomedical and/or behavioural intervention(s)) should include the Data and Safety Monitoring Plan (DSMP). The purpose of DSMP is to provide a framework for appropriate oversight and monitoring of the conduct of clinical trials to ensure the safety of participants and the validity and integrity of the data. It involves involvement of all investigators in periodic assessments of data quality and timeliness, participant recruitment, accrual and retention, participant risk versus benefit, performance of trial sites, and other factors that can affect study outcome.

Trial Monitoring

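### The protocol foresees a national campaign with another typhoid conjugate vaccine, but its definitions allow only vaccinated or unvaccinated and no described step records a later non-study dose

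*Protocol*

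**What the plan says.** **The campaign.** The protocol's Background of the Project states: "Currently, GAVI approved the vaccination campaign in Bangladesh to cover children aged 9 months to <16 years". It says rollout is expected soon and argues that a randomised trial would therefore be unethical. The paragraph on Vi-CRM names that product, not the study vaccine, as the likely campaign vaccine.

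**The cohort.** Inclusion criteria for vaccination: "Participants aged between 6 months to 15 years (i.e. up to 15 years 364 days) at the time of vaccination". Only children aged 6 to under 9 months fall outside the campaign's age range.

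**The exposure.** Cases and controls are both defined by "symptoms developed >14 days after vaccination, or, if unvaccinated, >14 days after the midpoint of the vaccination period" (Data Analysis, Culture-positive case and Culture-negative control). The model is fitted "taking non-receipt of vaccine as the referent category for assessment of vaccine protection" (Statistical analysis), and the shell table has columns only for vaccinees and non-vaccinees.

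**What is recorded.** The one rule on other typhoid vaccines is an exclusion applied at study vaccination: "Has knowingly received a typhoid vaccine in the past". Entry to surveillance asks for "Participants information, available in the listing database", consent, fever and age. Periodic household visits are described as serving "to remind them to seek treatment at the Maniknagar field office if their children (both vaccinees and non-vaccinees) develop a fever". The only home visit described within surveillance is for cases: "Blood culture-positive patients will be visited at home to confirm their identity, and collect information about their illness". Under Baseline listing, immunisation cards are photographed to confirm age. Under Screening and eligibility assessment, the timing of previous vaccines is asked about at the study vaccination visit only.

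**The concern.** The protocol relies on an imminent rollout to justify its design but does not carry that rollout into the exposure variable. There are two routes to misclassification.

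1. A study non-vaccinee who later takes a campaign dose stays in the referent.
2. A child refused the study vaccine because of an earlier typhoid vaccine still meets every surveillance criterion, and so also falls into the referent.

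The definitions do not say *study* vaccine, but the 14-day rule is tied to the study's vaccination period and the only vaccination record described is the study's. If a campaign dose were instead counted as vaccinated, the estimate would pool two products, so the gap remains on either reading.

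At stake are the primary VE estimate and the secondary comparison of the first and second six months. VE is biased toward zero when uptake is mainly in non-vaccinees or when the dose adds little in vaccinees. If contamination is heavier in the second half, stable protection can look like waning.

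**Working it through.** **Inputs from the protocol.** About 92,000 eligible children and about 60,000 vaccinated (Project Summary), so about 32,000 non-vaccinees. VE 80%, coverage 65%, 4 controls per case, total CI width 20 points, and incidence 230 per 100,000 person-years in the unvaccinated (Sample Size Calculation).

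**The plan's own figure.**
- Vaccinated share in cases: p1 = 0.65 × 0.2 / (0.65 × 0.2 + 0.35) = 0.271.
- Variance per case of the log odds ratio: 1/p1 + 1/(1 − p1) + [1/0.65 + 1/0.35]/4 = 6.163.
- Required standard error: asinh(0.20/(2 × 0.20))/1.96 = 0.2455.
- Cases: 6.163/0.2455² = 102.2, so 103 cases and 412 controls. This matches the protocol.
- Expected cases in one year: 32,000 × 0.0023 + 60,000 × 0.0023 × 0.2 = 73.6 + 27.6 = 101.2, so there is no reserve.

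**Bias model.** Let s be the share of the window after the campaign, u0 and u1 the uptake in study non-vaccinees and vaccinees, and b the extra proportional benefit in vaccinees. Assume the other TCV is 80% effective, and ignore the 14-day lag:

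Apparent VE = 1 − 0.2 × (1 − s·u1·b) / (1 − s·u0·0.8)

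The campaign date, the uptake, the other vaccine's effectiveness and b are all assumptions.

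| Scenario | One year | Second six months |
|---|---|---|
| Campaign after surveillance (s = 0) | 80% | 80% |
| Month 6, u0 = 0.5, b = 0 | 1 − 0.2/0.80 = 75.0% | 1 − 0.2/0.60 = 66.7% |
| Month 6, u0 = 0.7, b = 0 | 1 − 0.2/0.72 = 72.2% | 1 − 0.2/0.44 = 54.5% |
| Month 6, u0 = u1 = 0.7, b = 0.5 | 1 − 0.165/0.72 = 77.1% | 1 − 0.13/0.44 = 70.5% |
| Month 6, u0 = u1 = 0.7, b = 0.8 | 80% | 80% |
| Month 9, u0 = 0.3, b = 0 | 1 − 0.2/0.94 = 78.7% | not shown |
| Month 3, u0 = 0.9, b = 0 | 1 − 0.2/0.46 = 56.5% | not shown |

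In the month-6 rows the first six months stay at 80%.

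**Threshold.** With b = 0, overall VE falls by more than 10 points, the planned half-width, when 0.2/(1 − 0.8x) > 0.3. This gives x = s·u0 > 0.417, which means uptake above 0.417/0.5 = 83% for a month-6 campaign or 0.417/0.75 = 56% for month 3. Within the second six months of the month-6 case (s = 1), uptake above 42% is enough.

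**Campaign before or during study vaccination.** Here s = 1 throughout and recipients are refused the study vaccine. With 30% of non-vaccinees covered, VE = 1 − 0.2/0.76 = 73.7%. With 70% covered it is 54.5%. Both halves are affected alike, so there is no false waning.

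**Vaccination before the study.** Study area says no TCV campaign has been held there. Suppose 1% to 5% of all 92,000 children had been vaccinated and all fell into the referent. They would be 920/32,000 = 2.9% to 4,600/32,000 = 14.4% of non-vaccinees, and VE would be 79.5% to 77.4%. This route is minor.

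**The case against.** **Overlap is unproven.** The Background says only that rollout is near, with no date and no mention of these wards. The 22 months from proposed start to end also include set-up and analysis. This stands, and it makes the point conditional.

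**Silence is weak evidence.** The surveillance section lists no data items at all, not even those needed for the clinical exclusion rule or the covariates. CRF content sits elsewhere and may include vaccine history. This is fair, but nothing in the protocol requires the item. Any history taken only at the described home visit would cover cases and not controls.

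**Much of this belongs in the SAP.** Choosing exclusion, censoring or a separate exposure level is indeed SAP work, as is a sensitivity analysis. The SAP cannot, however, use an exposure that was never collected.

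**The leading scenario is adverse.** Nothing suggests an age-based campaign would skip study vaccinees. With equal uptake the overall VE is 77% to 80%, and even the 72% case lies within the planned ±10 points. This stands for the overall estimate. The second-six-month estimate is more exposed.

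**Conclusion.** The concern holds and should be fixed, with medium confidence because the timing is unknown. The protocol foresees widespread use of another TCV in almost its whole cohort, defines exposure in two states, and requires no record of a later non-study dose.

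Assuming both vaccines are 80% effective and vaccinees gain nothing from a second product, apparent overall VE is 57% to 79% for a campaign between months 3 and 9 with 30% to 90% uptake in non-vaccinees. The clearest damage is to the period comparison: 80% against 55% in the month-6, 70% case with no true waning. There is no bias if the campaign follows surveillance, or if uptake and proportional benefit are equal in both groups. The sample size is correct on its own inputs and is not in dispute.

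**What to change.** 1. **Surveillance for enteric fever:** at every surveillance enrolment, before the culture result is known, record any non-study typhoid vaccine, its product and its date. Check cards where possible and ask vaccinees and non-vaccinees the same question.
2. **Case and control definitions and Statistical analysis:** define exposure as the study vaccine and the referent as no typhoid vaccine of any kind before the focal time. Handle recipients of another TCV, including children refused the study vaccine for that reason, identically in cases and controls. Whether to exclude them or give them a separate exposure level can be left to the SAP.
3. **Sensitivity analysis:** restrict to focal times before the local campaign began.

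**Cost.** Collection needs one or two CRF items, and the definitions need two sentences. The analysis loses precision. The figures below use the unmatched variance 1/(n·p1·q1) + 1/(4n·p0·q0), with q = 1 − p, p0 the vaccinated share in controls and p1 recomputed from p0.

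| Situation | Cases | p0 | 95% CI for VE | Width (points) |
|---|---|---|---|---|
| Planned | 103 | 0.65 | 67.7% to 87.6% | 19.9 |
| Month 6, u0 = 0.7, u1 = 0: 73.6 × 0.65 + 27.6 | 75.4 | 0.743 | 65.9% to 88.3% | 22.4 |
| Month 6, u0 = u1 = 0.7: 101.2 × 0.65 | 65.8 | 0.652 | 63.6% to 89.0% | 25.4 |
| Month 3, 90% uptake in both: 101.2 × 0.325 | 32.9 | 0.652 | 53.3% to 91.4% | 38.1 |
| Pre-campaign only, month 6: 101.2 × 0.5 | 50.6 | 0.652 | 60.4% to 89.9% | 29.5 |

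After a campaign, the referent is children who took neither vaccine and may be selected. If their typhoid odds are k times those of non-vaccinees as a whole, second-half VE is 1 − 0.2/k: 75% at k = 0.8 and 84% at k = 1.25 (assumed range). Selection would have to reach k = 0.44 to do as much harm as the 54.5% obtained by doing nothing in the month-6, 70% case.
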